4. GENERAL STATISTICAL ANALYSIS CONSIDERATIONS

Unless otherwise stated, the following conventions will be applied when presenting summary-level statistics for data:

- Continuous variables will be summarized within each treatment group, presenting the following summary statistics: the sample size (i.e., the number of observations with an available value of the variable), arithmetic mean, sample SD, median, minimum, maximum, first quartile (Q1), and third quartile (Q3).
- Categorical data will be summarized within each treatment group by frequency (i.e., the number of observations within each level of the categorical variable in a given treatment group). All levels of the categorical variable will be included. If there are observations where the level of the categorical variable is missing, a separate category titled “Missing” will be created. For categorical variables that are ordinal in nature, the order in which the levels of the categories are displayed will be consistent with a natural ordering of the category levels. Percentages will also be calculated for each level of the categorical variables with respect to the total sample size for the respective treatment group. Patients with missing data will be included in calculations of percentages unless otherwise specified.

When stratification information is used in data summaries or analyses (e.g., in summaries of baseline demographic or disease characteristics or when used as covariates in statistical models), region and chronic systemic corticosteroid use at screening will be based on the values entered into the interactive voice response system [IVRS]/interactive web response system [IWRS]. Oral antifungal use at screening will be based on adjudication of the prior medications recorded on the Prior and Concomitant Medications electronic case report form (eCRF) as performed by the clinical team of the Sponsor.

All analyses will pool adult and adolescent participants.

Baseline measurements are defined as the Day 1 (i.e., day of first dose of study drug) value for each parameter. If a Day 1 value is not available for a given parameter, then the most recent screening value will be used as the baseline measurement, when available. For patients who are randomized but not treated, the most recent measurement on or prior to the day of randomization will be used as the baseline measurement.

The following rules will be used to determine the baseline measurement based on collected date and time information:

1. For safety data (e.g., vital signs, electrocardiography, and laboratory), pharmacokinetic (PK) data, ADA data, spirometry data, and FeNO measurements, both the date and time of the measurement will be compared to the date and time of the first dose of study drug to determine the baseline measurement. Baseline measurements are those that occur prior to administration of the first dose of study drug. If the time of the measurement is not available, this data will be considered to be treatment-emergent, that is, occurring after the first dose of study drug, and will not be eligible to be considered for the baseline measurement. If the time of administration of the first dose of study drug is not available, all laboratory, PK, and ADA data occurring on the date of administration of the first dose of study drug will be considered to be treatment-emergent and will not be eligible to be

considered for the baseline measurement. If there are multiple Day 1 measurements that are eligible to be considered for the baseline measurement, the most recent value will be considered the baseline measurement (with the exception of spirometry and FeNO data, which have unique rules for handling multiple measurements on the same date as described in Section 7).

2. For all other data, the date of the measurement will be compared to the date of the first dose of study drug (i.e., no time information will be used) to determine the baseline measurement.

For laboratory data, if a measurement falls below the lower limit of quantification (LLOQ) or limit of linearity, half of the lower limit value (e.g., LLOQ/2) will be used for quantitative analyses. For data above the upper limit of quantification (ULOQ) or limit of linearity, the upper limit value (e.g., ULOQ) will be used for quantitative analyses.

All data manipulations and analyses will be performed using [REDACTED]
[REDACTED]

5. PATIENT DISPOSITION

The number of patients included in and excluded from the FAS, SAF, PKAS, AAS, and NAS analysis sets will be presented by treatment group. Patients excluded from each analysis set will be further summarized by reason for exclusion.

The number of randomized patients with at least one important protocol deviation will be presented by treatment group. Patients with at least one important protocol deviation will be further summarized by deviation category and description of deviation. A separate table will be provided summarizing the number of patients with important protocol deviations due to COVID-19 by treatment group. Corresponding percentages with respect to the number of randomized patients in each treatment group will be provided for these summaries.

5.1. Screening Dispositions

The number of enrolled patients (equivalently, screened patients, that is, patients who signed the informed consent/assent form [ICF]) who are randomized (i.e., assigned a randomization number in the IVRS/IWRS) and the number of enrolled patients who screen-fail (i.e., were not assigned a randomization number in the IVRS/IWRS) will be presented. Patients who screen-fail will be summarized by reason for screen-failure (including COVID-19-related reasons). If applicable, the number of patients who are improperly randomized (i.e., did not meet all inclusion criteria or met one or more exclusion criteria yet were assigned a randomization number in the IVRS/IWRS) will also be displayed. The corresponding percentages with respect to the total number of enrolled patients will also be presented.

5.2. Treatment Period Dispositions

The disposition of all randomized patients during the treatment period will be displayed by treatment group (as randomized). The number of treated patients (i.e., patients who received at least 1 dose of study drug) and the number of patients who complete the treatment period will be presented. A patient is considered to have completed the treatment period if they have an end of treatment (EOT) visit. As patients who discontinue study drug are allowed to remain in the study, the number of treatment period completers who remained on study drug throughout the entirety of the treatment period and those who permanently discontinued study drug early will be reported. Patients who permanently discontinued study drug early will be further summarized by reason for early study drug discontinuation (including COVID-19-related reasons).

The number of treatment period completers who proceed into the follow-up period will be reported. A patient will be considered to have entered the follow-up period if they had an EOT visit and the patient's date of last contact is after the date of the EOT visit. The disposition of patients who enter the follow-up period is described in Section 5.3.

Lastly, the number of patients who discontinue from the study during the treatment period (i.e., who have an early termination visit and no EOT visit in the database) will be presented. Patients who discontinue from the study early will be further summarized by reason for early discontinuation from the treatment period (including COVID-19-related reasons).

Corresponding percentages with respect to the number of randomized patients in each treatment group will also be presented for the aforementioned treatment period disposition statuses.

5.3. Follow-up Period Dispositions

For patients who complete the treatment period and enter the follow-up period (as defined in Section 5.2), the number of patients who complete the follow-up period (i.e., have an EOS visit) and those who discontinue from the follow-up period early will be reported. Patients who discontinue from the follow-up period early will be further summarized by reason for early discontinuation from the follow-up period (including COVID-19-related reasons).

Corresponding percentages for these follow-up period disposition statuses will also be provided, using the number of randomized patients who completed the treatment period and entered the follow-up period in each treatment group as the denominator.

6. DEMOGRAPHICS AND BASELINE CHARACTERISTICS

6.1. Demographics

The following demographic variables will be summarized descriptively by treatment group and overall (i.e., all patients combined) for the FAS population:

- Age (years) at screening
- Age category at screening (<18 years, ≥ 18 years to <40 years, ≥ 40 years to <65 years, ≥ 65 years)
- Sex (Male, Female)
- Race (American Indian or Alaska Native, Asian, Black or African American, Native Hawaiian or Other Pacific Islander, White, Other, Not Reported)
- Ethnicity (Hispanic or Latino, Not Hispanic or Latino, Not Reported, Unknown)
- Region (Asia, Eastern Europe, Western Countries)
- Baseline weight (kg)
- Baseline weight category (<60 kg, ≥ 60 kg)
- Baseline height (cm)
- Baseline body mass index (BMI) (kg/m^2)
- Baseline BMI category (<25 kg/m^2 , ≥ 25 to <30 kg/m^2 , ≥ 30 kg/m^2)

6.2. Screening/Baseline Disease Characteristics

The following disease characteristics will be summarized descriptively by treatment group and overall for the FAS population:

- Systemic corticosteroid use at screening (Yes, No)
- OAF use at screening (Yes, No)
- Baseline peripheral eosinophil count ($10^9/\text{L}$)
- Baseline peripheral eosinophil count category (< $0.15 \times 10^9/\text{L}$, $\geq 0.15 \times 10^9/\text{L}$)
- Baseline peripheral eosinophil count category (< $0.3 \times 10^9/\text{L}$, $\geq 0.3 \times 10^9/\text{L}$)
- Baseline FeNO (ppb)
- Baseline FeNO category (<20 ppb, ≥ 20 to <35 ppb, ≥ 35 ppb)
- Baseline pre-bronchodilator FEV1 (L)
- Baseline pre-bronchodilator FEV1 category (≤ 1.5 L, > 1.5 L)
- Baseline pre-bronchodilator percent predicted FEV1 (%)
- Baseline pre-bronchodilator percent predicted FEV1 category (<50%, $\geq 50\%$)
- [REDACTED]
- [REDACTED]
- [REDACTED]

- Baseline FEV1 reversibility (L)
 - Baseline FEV1 reversibility will be derived as baseline post-bronchodilator FEV1 minus baseline pre-bronchodilator FEV1
- Baseline percent FEV1 reversibility (%)
 - Baseline percent FEV1 reversibility will be derived as (baseline post-bronchodilator FEV1 minus baseline pre-bronchodilator FEV1) divided by baseline pre-bronchodilator FEV1 and multiplied by 100
- [REDACTED]
- [REDACTED]
- Baseline serum total IgE (IU/mL)
- Baseline Asthma Control Questionnaire 5-item version (ACQ-5) score
- Baseline St. George's Respiratory Questionnaire (SGRQ) total score
- Number of severe respiratory exacerbations requiring treatment with systemic corticosteroids in the 12 months prior to the screening visit (≤ 1 , 2, > 2 , Unknown, Missing)
 - For each patient, the number of severe respiratory exacerbations requiring treatment with systemic corticosteroids in the 12 months prior to the screening visit will be obtained from the question “Has the subject experienced ≥ 1 severe respiratory exacerbation requiring treatment with systemic corticosteroids within 12 months prior to the screening visit” and the subsequent follow-up question “If Yes, how many severe respiratory exacerbations required treatment in the past 12 months” on the Medical History eCRF. For patients who answer the initial question as “No”, the number of severe respiratory exacerbations requiring treatment with systemic corticosteroids in the 12 months prior to the screening visit will be set to 0. For patients who answer the initial question as “Yes”, the value entered for the subsequent follow-up question will be the number of severe respiratory exacerbations requiring treatment with systemic corticosteroids in the 12 months prior to the screening visit. If the initial question is not answered, but a value is entered for the subsequent follow-up question, the value entered will be the number of severe respiratory exacerbations requiring treatment with systemic corticosteroids in the 12 months prior to the screening visit. If the initial question is answered as “Yes” but no value is entered for the subsequent follow-up question, the patient will be categorized as “Unknown”. If neither question is answered, the patient will be categorized as “Missing”.

6.3. Medical History

Patient medical histories will be coded using the Medical Dictionary for Regulatory Activities (MedDRA®). The frequency and percentage of each medical history event will be summarized by system organ class (SOC) and preferred term (PT) by treatment group and overall for the FAS population.

7. EFFICACY DATA

Efficacy endpoints will be analyzed using the FAS.

Per protocol, spirometry should be performed prior to administration of study drug and in accordance with American Thoracic Society (ATS)/European Respiratory Society (ERS) guidelines ([Miller, 2005](#)).

For pre-bronchodilator measured parameters, including FEV1, [REDACTED] spirometry will be performed after a washout period of bronchodilators according to their action duration. Examples of washout periods include withholding the last dose of salbutamol/albuterol or levosalbutamol/levalbuterol for at least 6 hours, withholding the last dose of LABA for at least 12 hours (ultra-long-acting LABA, such as vilanterol, should be withheld for at least 24 hours), withholding the last dose of ipratropium for at least 8 hours, and withholding the last dose of LAMA for at least 24 hours. Withholding times will be verified before performing the measurements. Note that when both pre- and post-bronchodilator spirometry are assessed, the post-bronchodilator spirometry should be performed 30 minutes after administration of 2 to 4 puffs of albuterol or another SABA.

At all visits, spirometry should be performed in the morning if possible, but if the test can only be done at a different time of the day, the testing should be done at approximately the same time of the day at each visit throughout the study.

A spirometer that meets the ATS/ERS recommendations will be used. The same spirometer and standard spirometric techniques, including calibration, will be used to perform spirometry at all visits and, whenever possible, the same person should perform the measurements. Three measurements fulfilling the ATS acceptability and repeatability criteria should be obtained at every visit, if possible.

Description of the selection of the “best” FEV1, [REDACTED] values for the purposes of the efficacy analyses is provided in [Appendix 14.4](#). Selection of the “best” FeNO value for the purposes of the efficacy analyses is also described in [Appendix 14.4](#). The acceptability criteria must be applied before the repeatability criteria. Unacceptable maneuvers must be discarded before applying the repeatability criteria. If a patient fails to provide repeatable and/or acceptable maneuvers, an explanation should be documented.

Unless otherwise specified, statistical testing will be performed using 2-sided tests with a nominal Type 1 error of 0.05. Two-sided confidence intervals (CIs) will be at the nominal 95% level unless otherwise specified.

7.1. Description of Efficacy Data

7.1.1. Pre-bronchodilator FEV1

The measurement used for the primary efficacy analysis is pre-bronchodilator FEV1. Pre-bronchodilator FEV1 is collected at screening, baseline, Weeks 2, 4, 8, 12, 24, 36, 44, and at EOT and EOS. For patients receiving OCS at baseline, pre-bronchodilator FEV1 is also collected at Weeks 6, 10, 14, and 16 when these visits are performed in-clinic.

The primary efficacy endpoint is the absolute change from baseline in pre-bronchodilator FEV1 compared to placebo at Week 24.

7.1.2. Severe Respiratory Exacerbations

Occurrences of severe respiratory exacerbations are recorded during the entirety of the study duration (i.e., from screening through post-treatment follow-up). A severe respiratory exacerbation is defined as new onset of symptoms or clinical worsening of respiratory symptoms requiring systemic corticosteroid treatment for ≥ 3 consecutive days; for patients who are on maintenance systemic corticosteroids, at least double the dose of maintenance systemic corticosteroids for ≥ 3 consecutive days (with or without antibiotic therapy if indicated). Per protocol, the start dates of severe respiratory exacerbation events must occur ≥ 28 days apart to be considered as distinct events. A secondary efficacy endpoint is the annualized rate of severe respiratory exacerbations over the 24-52-week treatment period.

Another secondary efficacy endpoint is the annualized rate of ABPA-related exacerbations over the 24-52-week treatment period. ABPA-related exacerbations are defined as severe respiratory exacerbations (as defined above) that are associated with a doubling of serum total IgE from the prior pre-exacerbation value. Per protocol, patients who experience a severe respiratory exacerbation will have, as soon as possible, an unscheduled visit at the site for the collection of a blood sample for serum total IgE measurement. The serum total IgE value from this unscheduled visit (or the next available measurement if the unscheduled visit was not performed or if the blood draw from the unscheduled visit did not result) will be used to determine if a doubling of the serum total IgE from the prior pre-exacerbation value occurred. Only serum total IgE measurements collected within 30 days after the severe respiratory exacerbation (i.e., with date of serum total IgE blood draw – start date of severe respiratory exacerbation event + 1 ≤ 30) will be considered valid for the purposes of determining whether a doubling of serum total IgE occurred. If the serum total IgE measurement is collected beyond 30 days after the severe respiratory exacerbation event or if no post-exacerbation serum total IgE measurement is available, the severe respiratory exacerbation will be considered to be not ABPA-related for the purposes of analysis. The pre-exacerbation value is defined as the value of the most recent IgE measurement collected prior to the start date/time of the severe respiratory exacerbation event.

The annualized rate of severe respiratory exacerbations requiring either hospitalization or observation for >24 hours in an ED/urgent care facility over the 24-52-week treatment period is also a secondary efficacy endpoint.

For each of the aforementioned respiratory exacerbation efficacy endpoints, severe respiratory exacerbations will be determined based on the information entered in the Adverse Event eCRF. Specifically, adverse event records with verbatim term that includes the text “severe respiratory exacerbation” will be selected for analysis. To determine whether a severe respiratory exacerbation is ABPA-related, the date/time of each severe respiratory exacerbation event recorded on the Adverse Event eCRF will be used to identify the prior and subsequent serum total IgE measurements. To determine, whether a severe respiratory exacerbation event required hospitalization or observation for >24 hours in an ED/urgent care facility, the information entered in the “Comment” field on the Adverse Event eCRF will be used; sites will enter the text “HEDURG: Yes” into the comment field to indicate severe respiratory exacerbations requiring hospitalization or observation for >24 hours in an ED/urgent care facility, as instructed in the Clinical Completion Guidelines (CCGs).

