#### 4.1.2. Secondary Endpoints

The secondary endpoints are:

- Annualized rate of severe respiratory exacerbations, defined as new onset of symptoms or clinical worsening of respiratory symptoms requiring systemic corticosteroid treatment for ≥3 consecutive days; for patients who are on maintenance systemic corticosteroids, at least double the dose of maintenance systemic corticosteroids for ≥3 consecutive days (with or without antibiotic therapy if indicated) over the 24- to 52-week treatment period
- 2. Annualized rate of ABPA-related exacerbations, defined as severe respiratory exacerbations (as defined above) that are associated with a doubling of serum total IgE from the prior pre-exacerbation value, over the 24- to 52-week treatment period
- 3. Annualized rate of severe respiratory exacerbations requiring either hospitalization or observation for >24 hours in an ED/urgent care facility during the 24- to 52-week treatment period
- 4. Change from baseline in ACQ-5 over the 24- to 52-week treatment period
- 5. Change from baseline in SGRQ total score over the 24- to 52-week treatment period
- 6. Percentage of participants achieving a reduction in the SGRQ score of 4 points or greater from baseline to weeks 12, 24, 36, and 52
- 7. Percent change from baseline in total IgE in serum over the 24- to 52-week treatment period
- 8. Percent change from baseline in *A fumigatus*-specific IgE in serum over the 24- to 52week treatment period
- 9. Percent and absolute change from baseline in FeNO over the 24- to 52-week treatment period
- 10. Incidence of treatment-emergent adverse events (TEAEs) from baseline through the end of treatment (week 24 to 52)
- 11. Immunogenicity of dupilumab, as determined by the incidence, titer, and clinical impact of treatment-emergent ADA to dupilumab over time
- 12. Concentrations of functional dupilumab in serum by treatment regimen at each assessment time point from baseline to the end of study

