#### Figure 1: Study Flow Diagram

Note: Upon implementation of amendment 3, the treatment period for all participants will be a minimum of 24 weeks and a maximum of 52 weeks. The week of EOT and EOS will vary accordingly.

NOTE: If there are restrictions to the clinical study as a result of the COVID-19 pandemic, it may be necessary to adjust the visit schedule, convert in-person visits to telephone contacts, and postpone study procedures until the next available study visit. It is necessary that the randomization visit (V2) occur in the clinic. All temporary mechanisms utilized, and deviations from planned study procedures in response to COVID-19 are to be documented as being related to COVID-19 and will remain in effect only for the duration of the public health emergency. Once local COVID-19 conditions resolve, all study visits and procedures should follow the schedule of events as specified in the Schedule of Events (Table 1).

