#### 9.2.2.3. Allergic Bronchopulmonary Aspergillosis-Related Exacerbations

Allergic bronchopulmonary aspergillosis-related exacerbations will be recorded by the investigator and are defined as a severe respiratory exacerbation (as defined in Section 9.2.2.1) associated with a doubling of serum total IgE value compared to the closest value before the onset of the exacerbation. For all respiratory exacerbations, patients will be required to have, as soon as possible, an unscheduled visit at the site for the collection of a blood sample for serum total IgE measurement.

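### Severe exacerbations with no IgE within 30 days are counted as not ABPA-related, so the secondary endpoint 2 rate can only be biased downward, by an amount the documents do not determine

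*SAP*

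**What the plan says.** Protocol 4.1.2 lists secondary endpoint 2 as "Annualized rate of ABPA-related exacerbations, defined as severe respiratory exacerbations (as defined above) that are associated with a doubling of serum total IgE" from the value before the exacerbation. Protocol 9.2.2.3 requires the blood draw that decides this: "For all respiratory exacerbations, patients will be required to have, as soon as possible, an unscheduled visit" at the site. It sets no time limit on the draw and has no rule for a missing one.

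SAP 7.1.2 adds three rules:

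- A fallback: the IgE from the unscheduled visit is used, "or the next available measurement if the unscheduled visit was not performed" or if its sample gave no result.
- A validity window: "Only serum total IgE measurements collected within 30 days after the severe respiratory exacerbation" count, defined as draw date minus start date plus 1 being at most 30.
- A default: an event whose IgE was drawn later than that is set to not ABPA-related. A missing value is handled the same way: "if no post-exacerbation serum total IgE measurement is available, the severe respiratory exacerbation will be considered to be not ABPA-related for the purposes of analysis".

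SAP 7.2.2 analyses endpoint 2 in the same way as all severe exacerbations. That is a negative binomial model giving a rate and 95% CI per group, with an offset running from first dose to the EOT visit or last contact. The offset is not shortened for events that could not be classified.

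SAP Section 4 has a general rule for laboratory data: "For data above the upper limit of quantification (ULOQ) or limit of linearity, the upper limit value (e.g., ULOQ) will be used for quantitative analyses".

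**The concern.** An event with no valid IgE has an unknown classification, and the plan records it as a negative one. The event leaves the numerator while its person-time stays in the denominator. For a per-arm rate this default is not conservative, because any error it makes lowers the reported rate.

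The fallback is weak late in treatment. SAP 7.1.11 schedules total IgE at Weeks 4, 8, 12, 24, 36, EOT and EOS. After Week 12 the gaps are 12 weeks or, for a patient treated to Week 52, 16 weeks, against a 30-day window. Late draws are foreseeable: during COVID-19 restrictions the note to Protocol Figure 1 says "it may be necessary to adjust the visit schedule, convert in-person visits to telephone contacts, and postpone study procedures until the next available study visit".

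Endpoint 2 is the exacerbation endpoint specific to ABPA and has its own secondary objective. The protocol's amendment history says secondary endpoints are no longer compared with placebo, so the absolute rate in each arm is the result. Its confidence interval would carry no sign that some events were never classifiable.

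**Working it through.** The documents give no event rate, count or power for this endpoint, so there is no planned figure to reproduce. The check asks how much of the follow-up the scheduled draws can cover when the unscheduled draw fails.

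**Inputs**
- Target days for scheduled IgE (SAP 7.1.11; SAP 11.4, Table 3): 29, 57, 85, 169, 253 and, for a patient treated to Week 52, EOT on day 365. For a 24-week patient, EOT is day 169.
- Window (SAP 7.1.2): an onset on day t is classifiable from a draw on day d if d ≥ t and d − t + 1 ≤ 30. Each draw therefore covers 30 onset days.
- Share of events whose unscheduled draw is missed or late, m: not given. A range of 10-40% is assumed.

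**Step 1. Onset days covered by scheduled draws alone**

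| Period | Days covered | Share |
|---|---|---|
| To Week 12 (days 1-85) | 85/85 | 100% |
| Weeks 12-24 (days 86-169) | 30/84 | 36% |
| Weeks 24-36 (days 170-253) | 30/84 | 36% |
| Weeks 36-52 (days 254-365) | 30/112 | 27% |

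Overall cover c:
- 24-week patient: (85 + 30)/169 = 115/169 = 68%
- 52-week patient: (85 + 30 + 30 + 30)/365 = 175/365 = 48%

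The EOS draw, 12 weeks after EOT, is too late for any event counted up to EOT.

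**Step 2. Effect on the rate**

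The classifiable share is s = (1 − m) + m·c. If onset is uniform over time and missingness is unrelated to ABPA status, planned rate / true rate = s, so the understatement is 1 − s = m(1 − c).

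| m | 24 weeks (1 − c = 0.320) | 52 weeks (1 − c = 0.521) |
|---|---|---|
| 0 | 0% | 0% |
| 10% | 3.2% | 5.2% |
| 20% | 6.4% | 10.4% |
| 40% | 12.8% | 20.8% |
| 100% | 32% | 52% |

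**Step 3. What bounds would show**

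Let p be the ABPA-related share among classifiable events, assumed to be 0.5. Per severe exacerbation, the all-no bound is p·s and the all-yes bound is p·s + (1 − s). With m = 20%:
- 52 weeks (s = 0.896): 0.45 to 0.55, where the plan would report 0.45
- 24 weeks (s = 0.936): 0.47 to 0.53, where the plan would report 0.47

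**Step 4. The ULOQ cap, if it applies to total IgE**

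A doubling registers only if min(post, ULOQ) ≥ 2 × min(pre, ULOQ). Once pre exceeds ULOQ/2, the right side exceeds ULOQ and the condition cannot be met. For assumed ULOQs of 2000, 5000 and 10000 IU/mL, that happens for pre-exacerbation values above 1000, 2500 and 5000. A grid check at ULOQ 5000 found false negatives only and no false positives. Protocol 3.3.1 reports a fall in total IgE of about 70% on dupilumab. With that fall, a dupilumab patient is affected only from baselines of about 3333, 8333 and 16667 (ULOQ/2 divided by 0.3), so capping would bear mainly on placebo.

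**The case against.** The strongest reply is that the draw is mandatory for every exacerbation and a fallback exists, so the default may hardly ever be used. That stands. The documents give no missed-draw rate, and if all draws are on time the effect is zero. The COVID-19 note is general and limited to the public health emergency; it is not evidence that exacerbation draws were missed.

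Other points also stand:

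- Only truly ABPA-related events are lost. A truly unrelated event set to no is classified correctly.
- The 27% figure needs the full gap from Week 36 to Week 52. Under the variable treatment period the gap can be shorter. An EOT at Week 40 falls 28 days after Week 36 and leaves no uncovered day in between.
- The endpoint is secondary, with no multiplicity control. Redacted text in SAP 7.2.2 follows the sentence on this endpoint, so a sensitivity analysis there cannot be excluded.
- The ULOQ cap is a general laboratory rule. The SAP places total IgE under biomarkers (7.1.11), omits it from the laboratory list in 10.2, and shows no ULOQ or dilution rule for it. A capped result is also a measured value, which is a different mechanism from a missing one.

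A reader might infer that the rule favours dupilumab. The documents do not support that. Protocol 8.7 keeps sites blinded and withholds post-treatment IgE results from them, so nothing suggests draws would be missed differently by arm. Capping, if it occurs, would mainly lower the placebo rate.

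What the reply does not answer is that the default works in one direction only and leaves no trace in the planned output.

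**Conclusion.** The point holds in a limited form. The rule can only bias the endpoint 2 rate downward. The size is unknown: zero with complete timely draws, and about 3-13% (24 weeks) or 5-21% (52 weeks) if 10-40% of draws are missed. Those figures rest on five assumptions: the missed share, uniform onset, missingness unrelated to ABPA status, draws on target days, and no help from IgE taken at other unscheduled visits.

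Two stronger readings go too far. One is that the plan does understate the rate; the documents show only that it can. The other is to take the thin cover after Week 12 as the size of the problem. That cover matters only for events whose unscheduled draw failed, and early events are fully covered.

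The ULOQ route is secondary and conditional, and cannot be sized. The primary FEV1 analysis is unaffected. The change is worth making because it is cheap, not because a large error has been shown.

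**What to change.** In SAP 7.1.2, classify each severe exacerbation as ABPA-related, not ABPA-related or unclassifiable, the last meaning no valid IgE within 30 days. In SAP 7.2.2, report the number unclassifiable in each arm. Give the annualized rate under both bounds, all unclassifiable events set to no and all set to yes, in place of the single default. The existing negative binomial model can be run on each count, with the existing descriptive fallback if it does not converge.

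State the ULOQ and any dilution rule for total IgE. If the Section 4 cap does apply, also treat as unclassifiable an event with a pre-exacerbation value above ULOQ/2 and a capped post value.

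Multiple imputation of event status is not requested; with about 30 patients per arm and probably few events, its value is debatable.

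The cost is SAP wording, minor programming, and a range where there would have been one figure. No new data are needed.
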